6.3 Analysis Visit

Analysis visit windows are defined as shown in Table 1 to determine the analysis value for each study visit. Measurements collected outside of the visit window will be considered missing for that study visit. For all patients with multiple values within a visit window, the value obtained closest to the target study day will be used. In the case of multiple observations equidistant to the study visit date, the later one will be used, unless otherwise noted. Only for screening visit, the earliest one will be used for analysis if multiple values were obtained within 28 days prior to randomization.

In regard to “after the invasive procedure”, which is the analysis visit for WHO Bleeding Scale, Portal Vein Thrombosis, and Portal Blood Flow, the allowance is within 3 days to 10 days after the first invasive procedure. In the case of multiple observations equidistant to the study visit date, the earlier one will be used, unless otherwise noted.

Table 1 Analysis Visit Windows

Study Day for Analysis	Allowance
Screening	Within 28 days prior to randomization
Day 1 (Baseline)	Within 7 days before initiation of study medication
Days 5-7	± 0 day
Day 8	± 0 day
Day 10	± 1 day
Days 12 and 14	+1 day
Days 17 and 21	-1 day to +2 days
Day 28	± 2 days
Day 35	-2 day to +7 days

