7.7.7 Laboratory Tests (Except for Platelet Count)

A list of clinical laboratory tests is shown in Table 7-4. Full details of all laboratory tests are provided in Appendix 2. Central Laboratory tests (except for platelet count) will be performed during the Screening period, and on Days 1 (ie, immediately before the first dose of study drug), 8*, 14, and 35 (or at drug withdrawal and/or early termination of assessment, if applicable).

Blood samples will be collected by the investigator or designee at the pre-specified time points. All samples will be sent to the central laboratory for processing. Full details of the sample collection, handling, labelling, storage, and shipping procedures will be specified in a separate manual.

The reference ranges provided by the central laboratory will be used to assess whether values are normal (ie, within the reference range) or abnormal (ie, outside the reference range).

Any abnormal changes from baseline (Day 1) will be assessed by the investigator or designee for clinical significance (see Section 7.8.9), with any clinically significant

findings recorded as an AE on the CRF.

* If laboratory tests are measured at drug withdrawal, laboratory tests on Day 8 are not necessary.

Table 7-4: Routine Laboratory Tests (Except for Immunological Test, Blood Thrombopoietin Concentration, and Platelet Count)

Test	Items Evaluated
Haematology (except for platelet count)	Red blood cell count, white blood cell count, haemoglobin, and haematocrit
Blood chemistry	aspartate aminotransferase (AST), alanine aminotransferase (ALT), lactate dehydrogenase, gamma glutamyl transferase, alkaline phosphatase, total bilirubin, bilirubin direct, indirect bilirubin, total protein, albumin, blood urea nitrogen, serum creatinine, sodium, potassium, chloride, and calcium
Blood coagulation/ fibrinolysis assay	Prothrombin time (international normalised ratio value), activated partial thromboplastin time, antithrombin III activity ^a , fibrinogen ^a , fibrin degradation products ^a , D-dimer ^a , protein C activity ^a , free protein S antigen ^a and von Willebrand factor activity ^a

^a Only at Screening.

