7.11 Allowable Time Window

All measurements and assessments will be performed according to the schedule provided in Appendix 1. If, for unavoidable reasons, study measurements and assessments are not possible at the specified time points, they should be performed within an allowable time window (see [Table 7-5](#)). Data collected outside of the allowable time window will be handled as missing data for that study visit.

Table 7-5: Allowable Time Window

Timing	Study Day	Allowance
Screening	After obtaining consent and before randomisation	After obtaining consent and within 28 days prior to randomisation ^a
Randomisation	Before initiation of study medication	Within 7 days before initiation of study medication
Before initiation of study medication	Day 1	Within 7 days before initiation of study medication ^b
Treatment period	Days 1-7	± 0 day
Post-treatment period	Day 8	± 0 day
	Day 10	± 1 day
	Days 12 and 14	± 1 day
	Days 17 and 21	-1 day to +2 days
	Day 28	± 2 days
	Day 35	-2 day to +7 days
At drug withdrawal	-	Within 2 days after the next day of final administration
At early termination of study assessment	-	Within 7 days after the day of early termination of study assessment

^a The result of the upper gastrointestinal endoscopy for the assessment of gastro-oesophageal varices can be used if the test is performed within 180 days before randomisation. The diagnostic imaging

(ultrasonography, CT, or MRI) for the assessment of splenomegaly can be used if the diagnostic imaging is performed within 28 days before randomisation. The diagnostic imaging (ultrasonography, CT, or MRI) for the assessment of portal vein thrombosis should be arranged as close to randomisation as possible; however, if gastro-oesophageal varices are treated, confirmation should be made after the treatment.

b Data obtained within 7 days before initiation of study medication can be used as baseline data (Day 1).

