10.6 Laboratory Tests

For laboratory tests listed in [Table 4](#), summary statistics of observations and their changes from baseline will be calculated at each scheduled time point (Days 1, 8, 14, 35 and last observation) by treatment group.

Table 4 List of Laboratory Tests

Test	Items Evaluated
Haematology (except for platelet count)	Red blood cell count, white blood cell count, haemoglobin, and haematocrit
Blood Chemistry	Aspartate aminotransferase (AST), alanine aminotransferase (ALT), lactate dehydrogenase, gamma glutamyl transferase, alkaline phosphatase, total bilirubin, bilirubin direct, indirect bilirubin, total protein, albumin, blood urea nitrogen, serum creatinine, sodium, potassium, chloride, and calcium
Blood Coagulation/Fibrinolysis Assay	Prothrombin time-international normalized ratio (PT-INR), activated partial thromboplastin time

Individual clinically significant abnormalities (ICSA) will be summarized based on criteria which are determined by reference to Common Terminology Criteria for Adverse Events (CTCAE) Version 4.0 (see [Appendix 4](#)). For each CTCAE term shown in Appendix 4, the number and proportion of patients with a laboratory test result classified as grade 2 or more will be calculated at each scheduled time point (Days 1, 8, 14, 35) by treatment group. In addition, the number and proportion of patients with a laboratory test result classified as grade 2 or more at least once after the initiation of study drug will be calculated. For the term “hyponatremia”, the number and proportion of patients with a laboratory test result classified as grade 3 or more will be summarized because the term doesn’t have criteria for grade 2. The upper limit of normal range for PT-INR is regarded as 1 if it will not be specified by the central laboratory.

The number and proportion of patients who met the following criteria for liver function abnormalities will be calculated at each scheduled time point (Days 1, 8, 14, 35) by treatment group. The number and proportion of patients with liver function abnormalities after the initiation of study drug will also be calculated.

- AST or ALT $\geq 3 \times$ upper limit of normal (ULN) and total bilirubin $\geq 2 \times$ ULN
- AST or ALT $\geq 3 \times$ ULN and PT-INR ≥ 1.5
- AST/ALT ≥ 3

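### SAP Table 1 narrows the Day 12 and Day 14 windows from the protocol's ±1 day to +1 day without declaring it, so compliant Day 13 laboratory samples miss the Day 14 tables and some early platelet counts are dropped

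*SAP*

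**What the plan says.** **Windows.** Protocol 7.11, Table 7-5, reads "Days 12 and 14 ± 1 day". SAP 6.3, Table 1, reads "Days 12 and 14 +1 day". All the other post-baseline visit rows (Days 5 to 7, 8, 10, 17, 21, 28 and 35) agree between the two tables.

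**Consequence of falling outside.** The protocol: "Data collected outside of the allowable time window will be handled as missing data for that study visit". The SAP: "Measurements collected outside of the visit window will be considered missing for that study visit". Each rule applies to its own document's window.

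**Several values in one window.** Under SAP 6.3, "the value obtained closest to the target study day will be used", and if two are equally distant, "the later one will be used, unless otherwise noted".

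**Schedule.** Platelet counts are due on Days 10, 12 and 14 (Protocol 7.5.2), and so are blood pressure and pulse rate (Protocol 7.7.5). Central laboratory tests after baseline are due on Days 8, 14 and 35 only (Protocol 7.7.7). SAP 10.6 follows this, with laboratory summaries "calculated at each scheduled time point (Days 1, 8, 14, 35 and last observation".

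**Declared changes.** SAP Section 13 lists two changes from the protocol: the added van Elteren analysis and the removal of significant TEAEs. The visit windows are not mentioned.

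**The concern.** A site that sees a patient one day early for Day 12 or Day 14 has followed the protocol, yet the analysis treats that visit as out of window. Two kinds of data are exposed.

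- **Laboratory tests.** Day 14 is the only laboratory time point between Day 8 and Day 35. A sample taken on Day 13 cannot count for Day 14, and there is no Day 12 laboratory summary to receive it.
- **Platelet counts.** These are taken around the time of the procedure and supply the by-visit responder rates, the time course, and the duration of counts at or above 50 × 10⁹/L. Duration is formally tested in the gatekeeping sequence. If the windows remove a valid count, the calculation interpolates across the gap.

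Because the narrowing is undeclared, a reader of the report would not know that compliant visits had been set to missing.

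**Working it through.** **Step 1. Day ranges implied by each table.**

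| Visit | Protocol Table 7-5 | SAP Table 1 |
|---|---|---|
| Day 10 | 9–11 | 9–11 |
| Day 12 | 11–13 | 12–13 |
| Day 14 | 13–15 | 14–15 |
| Day 17 | 16–19 | 16–19 |

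The protocol ranges overlap on Days 11 and 13. The SAP ranges do not overlap and leave no gap from Day 9 to Day 19.

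**Step 2. Laboratory tests.** A Day 13 sample lies inside the protocol's Day 14 range (13–15) and outside the SAP's (14–15). Day 13 does lie in the SAP's Day 12 range, but laboratory results are not summarised at Day 12. The sample therefore enters no by-visit summary.

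Neither document gives the rate of early visits. As an assumption, take 5%, 10% or 20% of Day 14 visits held on Day 13, with all 200 patients attending: 200 × 0.05 = 10, 200 × 0.10 = 20, 200 × 0.20 = 40 patients without a Day 14 value.

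**Step 3. Platelet counts.** List every compliant set of dates for the Day 10, 12 and 14 visits, strictly increasing. There are 3 × 3 × 3 = 27 combinations. Three put Days 10 and 12 both on Day 11, and three put Days 12 and 14 both on Day 13, which leaves 27 − 6 = 21. Then apply the SAP rules, assuming no counts other than these three.

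An early Day 12 visit (on Day 11) occurs in 2 × 3 = 6 patterns. An early Day 14 visit (on Day 13) with Day 12 held on Day 12 occurs in 3 more. In all 9, one count is dropped and one visit is empty:

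| Actual dates | Count dropped | Visit left empty |
|---|---|---|
| 9, 11, 13 | Day 9 | Day 14 |
| 9, 11, 14 | Day 9 | Day 12 |
| 9, 11, 15 | Day 9 | Day 12 |
| 9, 12, 13 | Day 13 | Day 14 |
| 10, 11, 13 | Day 11 | Day 14 |
| 10, 11, 14 | Day 11 | Day 12 |
| 10, 11, 15 | Day 11 | Day 12 |
| 10, 12, 13 | Day 13 | Day 14 |
| 11, 12, 13 | Day 13 | Day 14 |

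In 6 of the 9 an early count is itself dropped. In the other 3, Days 9 and 11 are equally far from Day 10, the later value wins, and the Day 9 count goes. The remaining 12 patterns lose nothing. The 21 patterns are not equally likely, so 9 of 21 is not a rate of loss.

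**Step 4. Effect on duration.** SAP 9.2.3 plots each count at its actual measurement date and sums the time at or above 50 along straight lines. A count filed under another visit keeps the same coordinates and contributes the same amount. Only a dropped count can change the result. An example with assumed counts, for dates 10, 12, 13: 30, 40, 46, 56, 58, 44 and 38 on Days 1, 8, 10, 12, 13, 17 and 21.

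- Upward crossing: 10 + 2 × (50 − 46)/(56 − 46) = 10.8, giving 12 − 10.8 = 1.2 days.
- With the Day 13 count: 1 day from Day 12 to Day 13, then 4 × (58 − 50)/(58 − 44) = 2.29 days. Total 1.2 + 1 + 2.29 = 4.49 days.
- Without it: 5 × (56 − 50)/(56 − 44) = 2.5 days. Total 1.2 + 2.5 = 3.7 days.

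The difference is about 0.8 days in this constructed case. The change is zero when the dropped count does not alter where the line stands relative to 50.

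**Step 5. Effect of simply restoring ±1 day.** No compliant pattern then leaves a visit empty, but one count can fill two visits. With dates 9, 11, 14, the Day 11 count would serve as both Day 10 and Day 12.

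**The case against.** The strongest defence is that +1 day is deliberate. Table 7-5 governs when visits may be held, and Table 1 governs which value represents a visit. The protocol does not say how to allocate a count that lies in two windows, and the SAP entry gives contiguous windows that remove the ambiguity. For platelet counts and vital signs this largely stands: allocation by date is a defensible choice. It does not explain the laboratory case, where no Day 12 visit competes for a Day 13 sample, and it does not excuse the silence in Section 13. A typographical slip for ± is possible, though the sign prints correctly in four other rows of Table 1.

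The defence can also say that little is lost, and much of that stands. Day 13 laboratory results remain in the patient listings. They can count in the SAP 10.6 summaries of grade 2 or more results and liver abnormalities at any time after the start of drug, since neither is tied to a visit. Clinically significant results are also recorded as adverse events. A reader might infer that safety data disappear altogether; the documents do not support that. What goes is the Day 14 by-visit value.

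A reader might likewise infer that filing an early platelet count under the wrong visit distorts duration. It does not, because SAP 9.2.3 uses actual dates.

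**Conclusion.** The mismatch is exact and undeclared, and it has a definite consequence for Day 14 laboratory tables: compliant Day 13 samples are left out of the by-visit means, the grade 2 or more counts and the liver-abnormality counts. For platelet counts, an early Day 12 or Day 14 visit costs one valid count and leaves one visit empty whenever all three visits are held on compliant dates. That affects by-visit responders and the time course, and duration through the dropped count alone. Vital signs at Days 12 and 14 are exposed in the same way.

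The size is unknown because the documents give no rate of early visits; 10 to 40 of 200 patients for the laboratory values rests on the assumed 5% to 20%. The primary endpoint depends on transfusion, rescue therapy and having the procedure, so it is not affected. Nothing in the documents suggests that early visits would differ between arms. This is worth correcting because it is cheap, not because it threatens the main conclusion.

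A reader might extend the point to Day 8, since the protocol says "If laboratory tests are measured at drug withdrawal, laboratory tests on Day 8 are not necessary", while the SAP holds Day 8 to ±0 days. The documents do not support that extension. Day 8 is ±0 days in both tables. The protocol says only that Day 8 tests are unnecessary after a withdrawal sample, not that the sample becomes Day 8 data. Labelling an earlier sample as Day 8 would misstate its timing.

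**What to change.** Before unblinding:

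1. In SAP Table 1, set the Day 14 window to ±1 day for laboratory tests. No overlap arises, because there is no Day 12 laboratory visit.
2. For platelet counts and vital signs, choose one of two rules and state it. Either assign each sample inside its protocol window to its nominal visit, with one sample serving one visit only, or keep the non-overlapping +1 day windows for by-visit tables and let the duration calculation use every platelet count taken within protocol windows. Restoring ±1 day alone is not enough, because one count could then fill two visits.
3. List the remaining difference from Protocol Table 7-5, with its reason, in SAP Section 13.

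The cost is an edit to Table 1, a sentence or two in SAP 6.3 and 9.2.3, an entry in Section 13, and a small programming change. No new data are needed.

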7.7.2 Portal Vein Thrombosis

Portal vein thrombosis will be assessed by the investigator or designee using diagnostic imaging (ultrasonography, CT, or MRI) during the Screening period, and between 3 and 10 days after the planned invasive procedure* in the Post-treatment period (Days 12 to 21). For assessment in the Screening period, the investigation should be arranged as close to randomisation as possible. However, for patients in whom gastro-oesophageal varices are treated, portal vein thrombosis will be confirmed using imaging performed after the treatment.

The imaging date and method, and the presence or absence of portal vein thrombosis will be recorded on the CRF. The independent safety committee will assess portal vein thrombosis (see Section 9.8.2).

* Even if the planned invasive procedure is postponed. In addition, if any additional invasive procedures are performed, diagnostic imaging should also be performed before and after the additional procedure for post-assessment of the initial and additional procedures.

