6.5.2 Baseline

The baseline value is defined as a value obtained on Day 1 before administration of the initial dose of study drug. If this value is missing, the most recent value obtained prior to Day 1 within the 7 preceding days will be used as the baseline value. Regarding body weight, height, and body mass index (BMI), the measurement at screening visit will be used as the baseline value.

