9.1.1.1 Subgroup Analysis

The primary endpoint will be analyzed separately for the following subgroups:

- Platelet count at baseline: $< 35 \times 10^9/\text{L}$, $\geq 35 \times 10^9/\text{L}$
- Received primary invasive procedure: Percutaneous RFA/MCT, Laparoscopic RFA/MCT, EVL, EIS, TACE, TAE, other, and not performed
- Sex: male, female
- Age: < 65 years, ≥ 65 years
- Baseline body weight: $< 75 \text{ kg}$, $\geq 75 \text{ kg}$
- Race: White, NonWhite
- Child-Pugh class: A, B, C

The number and proportion of patients will be calculated by treatment group. The proportion of patients will be reported and will be compared between the S-888711 and placebo groups by Fisher's exact test. In addition, the interaction between subgroup (except received invasive procedure and Child-Pugh class C) and treatment group will be tested with Breslow-Day test.

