Sampling for plasma drug concentration (Intensive PK) ⁿ							X	X	X														

a Except for a patient with drug withdrawn because of the administration stopping criterion (ie, platelet count $\geq 50 \times 10^9/L$ with an increase of $\geq 20 \times 10^9/L$ from baseline).

b Only necessary assessments will be performed.

c If platelet count on Day 5, 6 or Day 7 is $\geq 50 \times 10^9/L$ with an increase of $\geq 20 \times 10^9/L$ from baseline, a patient must stop taking study medication.

d Confirmed by upper gastrointestinal endoscopy. If data on upper gastrointestinal endoscopy are obtained within 180 days before randomisation, the data can be used.

e Confirmed by ultrasonography, CT, or MRI. If ultrasonography, CT, or MRI is performed within 28 days before randomisation, the image can be used for assessing the presence or absence of splenomegaly.

f Confirmed by ultrasonography, CT, or MRI in the Screening period and after the invasive procedure. The Screening investigation should be arranged as close to randomisation as possible. However, if gastro-oesophageal varices are treated, portal vein thrombosis will be confirmed with the image obtained after the treatment.

g Performed within 3 to 10 days after the invasive procedure. When any additional invasive procedure is performed, the assessment of bleeding events as graded on the WHO Bleeding Scale, portal vein thrombosis, and portal blood flow will be performed before and after the invasive procedure.

h Confirmed by Doppler ultrasonography (at Screening, the investigation should be as close to randomisation as possible).

i Blood samples will be collected before study medication.

j Antithrombin III activity, fibrinogen, fibrin degradation products, D-dimer, Protein C activity, free protein S antigen, von Willebrand factor activity will be performed only at Screening. Prothrombin time (international normalised ratio value) and activated partial thromboplastin time will be performed at Screening, Day 1, Day 8, Day 14, and Day 35.

k Administered after platelet count is confirmed and drug assignment.

l Performed between Days 9 and 14.

m All patients except for Intensive PK; pre-dose, 2 to 4 hours post-dose on Day 5, and pre-dose on Days 6 and 7.

n At least 20 patients; pre-dose, 2, 4, 6, 8 hours post-dose on Day 5, pre-dose on Days 6 and 7.

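### For patients whose varices are treated before randomisation, SAP 6.3 selects the pre-treatment portal vein image, while the protocol and SAP Appendix 1 name the post-treatment one

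*SAP*

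**What the plan says.** SAP 6.3 sets the general rule for repeated values: take the one nearest the target day and, for ties, "In the case of multiple observations equidistant to the study visit date, the later one will be used, unless otherwise noted". Screening is the exception: "Only for screening visit, the earliest one will be used for analysis if multiple values were obtained within 28 days prior to randomization".

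SAP 10.7 then counts portal vein thrombosis and portal flow direction by arm, once at screening and once after the primary procedure. It adds no rule of its own for repeated screening scans.

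The protocol treats the screening scan differently. Section 7.7.2 says of its timing that "the investigation should be arranged as close to randomisation as possible", and adds that "for patients in whom gastro-oesophageal varices are treated, portal vein thrombosis will be confirmed using imaging performed after the treatment". Footnote a of Protocol Table 7-5, attached to the Screening row, says the imaging "should be arranged as close to randomisation as possible; however, if gastro-oesophageal varices are treated, confirmation should be made after the treatment". The SAP repeats the rule in Appendix 1, footnote f: "if gastro-oesophageal varices are treated, portal vein thrombosis will be confirmed with the image obtained after the treatment".

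**The concern.** The SAP's selection rule and the documents' own statement of which image counts point in opposite directions. If a patient is scanned, has varices treated, and is scanned again before randomisation, the protocol relies on the second scan for thrombosis status and the SAP tabulates the first. The screening row of the SAP 10.7 table is the only pre-dose display of portal vein status, because Appendix 1 schedules no portal imaging on Day 1. A thrombosis already visible before dosing could therefore be shown as absent at screening and look new in the post-procedure row.

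**Working it through.** The plan gives no figure to reproduce here. The check is a comparison of the rules, followed by a look at which outputs depend on them.

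**1. Which image each rule selects.** Let A be a scan before variceal treatment and B a scan after it, both within 28 days before randomisation.

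| Source | Image that counts |
|---|---|
| SAP 6.3, as applied in SAP 10.7 | A |
| Protocol 7.7.2 | B |
| Protocol Table 7-5, footnote a (Screening row) | B |
| SAP Appendix 1, footnote f | B |

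Because footnote a belongs to the Screening row, the variceal sentence cannot be confined to imaging after the study procedure.

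**2. Whether A and B can both exist.** Exclusion 17 bars invasive procedures in the 14 days before randomisation but exempts treatment of varices. Treatment can therefore fall inside the 28-day window with a scan on each side. The documents do not say how often this happens.

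**3. Whether another rule overrides SAP 6.3.** SAP 6.5.2 takes the Day 1 value or, failing that, the most recent one in the preceding 7 days. That protects platelets, laboratory tests and vital signs. SAP 10.7 tabulates portal imaging at screening rather than at baseline, so SAP 6.3 governs it.

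**4. What changes in the table.** Exclusion 10 bars any portal vein thrombosis on imaging in the 28-day window or in the history.

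| A | B | Eligible? | SAP 6.3 shows | Post-treatment rule shows |
|---|---|---|---|---|
| absent | absent | yes | absent | absent |
| absent | present | no | absent | present |
| present | absent | no | present | absent |
| present | present | no | present | present |

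In the only eligible pattern the two rules agree. The second row is the harmful one: a patient enrolled in error whose pre-dose thrombosis is shown as absent. For portal flow, exclusion 11 bars absence of hepatopetal flow in the main trunk in the same window, so repeated Doppler results should also normally agree in eligible patients.

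**5. Age of the selected image.** The screening window allows up to 28 days before randomisation. Table 7-5 allows randomisation up to 7 days before first dose, so the literal upper bound is 28 + 7 = 35 days before first dose. Appendix 1 places randomisation on Day 1 before dosing, and the stated 63-day maximum leaves no such gap: 63 − 28 − 7 − 28 = 0. In ordinary conduct the bound is 28 days.

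**6. What does not depend on the rule.** The primary endpoint (SAP 9.1) is built from transfusion, rescue therapy and whether the procedure took place. Thrombotic events of special interest (SAP 10.2) are treatment-emergent events selected by standardised MedDRA queries. The post-procedure count in SAP 10.7 uses its own images.

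**The case against.** The best case for leaving the SAP alone is that the rule is prespecified, applies equally to both arms and acts only with repeats. A site that follows Protocol 7.7.2 may do a single scan, after variceal treatment, and the rule then never operates. SAP 10.7 plans separate counts, with no shift analysis and no test. Individual data are to be listed by patient (SAP 6.1), and the independent safety committee assesses portal vein thrombosis. All of this stands and limits the size of the problem. It does not remove the contradiction over which image counts.

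Several stronger readings are tempting, but the documents do not support them:

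- **That scheduling close to randomisation is itself a selection rule.** It says when to scan. Only the variceal sentence says which image counts.
- **That a Doppler after variceal treatment is required, or that portal flow is especially exposed.** Appendix 1 footnote h asks only for timing near randomisation, Protocol 7.7.3 has neither clause, and exclusion 11 constrains flow much as exclusion 10 constrains thrombosis.
- **That Child-Pugh class or body weight is misclassified.** SAP 9.1.1.1 lists "Child-Pugh class: A, B, C" although entry is limited to A and B, so one might picture a patient re-scored from C to B and analysed as C. For weight, SAP 6.5.2 says "the measurement at screening visit will be used as the baseline value". But both are scheduled once, no re-scoring is described, and no passage says the latest value should count.
- **That the trial's thrombotic event comparison hangs on this.** The Japanese phase 3 rate of 2.1% would give about 0.021 × 100 = 2.1 patients per arm if it carried over, but those events are counted as treatment-emergent events, whichever screening image is tabulated.

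**Conclusion.** The contradiction is genuine and narrow. For portal vein thrombosis in patients scanned both before and after variceal treatment, SAP 6.3 tabulates the image that Protocol 7.7.2, Table 7-5 footnote a and SAP Appendix 1 footnote f do not treat as confirming. Its practical size is low. It requires repeat imaging, whose frequency is not given, and it alters the displayed thrombosis or flow category mainly for patients enrolled despite exclusion 10 or 11. No efficacy conclusion and no adverse event count changes. This rests on two assumptions: that SAP 6.3 is applied as written to the SAP 10.7 tables, and that the eligibility criteria are otherwise enforced. It merits correction because a SAP should analyse the image its own schedule designates.

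**What to change.** Amend SAP 6.3, or add an exception in SAP 10.7, before unblinding. Where a screening assessment is repeated, the last one before randomisation is used; for portal vein thrombosis in patients whose varices were treated, the image taken after that treatment is used. It would help to footnote the table with the number of patients who had more than one screening image and the number whose category differed. The footnote would also keep visible the reverse pattern (thrombosis on the first scan only), which the new rule would show as absent.

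Applying the same last-value rule to portal flow, Child-Pugh class and body weight is an optional gain in consistency, in keeping with the most-recent-value principle of SAP 6.5.2. It does not repair a documented conflict.

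The cost is one SAP sentence and a small programming change. No new data are needed, and trial conduct is unaffected.
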